##### **9.4.6.1. Analysis of Adverse Events**

Analysis and reporting for AEs will be based on treatment-emergent AEs, including treatment-emergent SAEs (TESAEs) defined as an AE with onset on or after first dose of study drug administration in the Randomized Controlled Period. Treatment-emergent AEs and TESAEs will be summarized by MedDRA SOC and Preferred Term and by relationship to the study drug; TEAEs will also be summarized by severity. Patient-years adjusted event rates will be generated to characterize long-term safety profile.

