### 10.3. Appendix 3: Adverse Events: Definitions and Procedures for Recording, Evaluating, Follow-up, and Reporting

#### 10.3.1. Adverse Event Definition

Adverse Event Definition

• An AE is any untoward medical occurrence in a patient, temporally associated with the use of study drug, whether or not considered related to the study drug.

• NOTE: An AE can therefore be any unfavorable and unintended sign (including an abnormal laboratory finding), symptom, or disease (new or exacerbated) temporally associated with the use of study drug.

Events Meeting the AE Definition

• Any abnormal laboratory test results (hematology, clinical chemistry, or urinalysis) or other safety assessments (eg, ECG, radiological scans, vital signs measurements), including those that worsen from baseline, considered clinically significant in the medical and scientific judgment of the Investigator (ie, not related to progression of underlying disease).

• Exacerbation of a chronic or intermittent pre-existing condition including either an increase in frequency and/or intensity of the condition.

• New conditions detected or diagnosed after study drug administration even though it may have been present before the start of the study.

• Signs, symptoms, or the clinical sequelae of a suspected drug-drug interaction.

• Signs, symptoms, or the clinical sequelae of a suspected overdose of either study drug or a concomitant medication. Overdose per se will not be reported as an AE/SAE unless it is an intentional overdose taken with possible suicidal/self-harming intent. Such overdoses should be reported regardless of sequelae.

• "Lack of efficacy" or "failure of expected pharmacological action" per se will not be reported as an AE or SAE. Such instances will be captured in the efficacy assessments. However, the signs, symptoms, and/or clinical sequelae resulting from lack of efficacy will be reported as AE or SAE if they fulfil the definition of an AE or SAE.

Events NOT Meeting the AE Definition

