### Assessment of Intensity

The Investigator will make an assessment of intensity for each AE and SAE reported during the study and assign it to 1 of the following categories from National Cancer Institute CTCAE v5.0, published 27 Nov 2017:

- Grade 1: Mild (awareness of sign or symptom, but easily tolerated)
- Grade 2: Moderate (discomfort sufficient to cause interference with normal activities)
- Grade 3: Severe (incapacitating, with inability to perform normal activities)
- Grade 4: Life-threatening
- Grade 5: Fatal

Changes in the severity of an AE should be documented to allow an assessment of the AE duration at each level of intensity to be evaluated. Adverse events characterized as intermittent require documentation of onset and duration of each episode, if the severity of the intermittent event changes.

An event is defined as ‘serious’ when it meets at least 1 of the predefined outcomes as described in the definition of an SAE, NOT when it is rated as severe.

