#### **Assessment of Causality**

- If a patient dies during participation in the study or during a recognized follow-up period, the Investigator will provide Alexion with a copy of any post-mortem findings including histopathology.
- New or updated information will be recorded in the originally completed eCRF.
- The Investigator will submit any updated SAE data to Alexion within 24 hours of receipt of the information.

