**Table 5: Definition of TEAEs**

TEAE (RCP)	TEAE (OLE)
For RCP participants entering the OLE, a TEAE will be defined as any AE with onset on or after the first dose of IP in the RCP up to and including the day prior to the first OLE dose.	A TEAE will be defined as any AE with onset on or after first dose of OLE.
For RCP participants not entering the OLE, TEAE will be defined as an AE with onset on or after the first RCP dose of IP.	

If the time of the AE onset is available, it will be used to determine the treatment emergence by comparing with the time of the first study drug infusion, ie, if the AE onset time is prior to the time of infusion, it will not be considered as treatment-emergent.

Abbreviations: AE = adverse event; IP = investigational product; OLE = Open-Label Extension; RCP = Randomized Controlled Period; TEAE = treatment-emergent adverse event

The incidence, toxicity, and relationship to IP will be summarized by the treatment group. Specific AEs will be counted once for each participant for calculating percentages (e.g., overall, SOC, PT). In addition, if the same AE occurs multiple times for a participant, the highest severity and relationship to IP observed will be reported. All TEAEs will be summarized overall and categorized by MedDRA SOC and PT. The ordering of SOC will be alphabetical, and the ordering for PT will be most prevalent (using percentage) PT within each SOC based on the ravulizumab (RCP analysis) or total column (OLE). PTs with the same number of participants (eg, to break ties) will be further sorted by the number of events and then alphabetically.

Table 6 provides an overview of the tabular summaries of AEs for different periods, underlying analysis sets, and treatment group display convention. An “X” in the table represents that an analysis will be performed for the period. For incidence tables, the number of participants and percentage will be tabulated; percentages will be based on the number of participants in the respective treatment groups. For event-rate tables, the rate per 100 patient-years will be calculated as follows (see Table 4 for the definition of patient-years):

$$= 100 \times \frac{\text{Total number of TEAEs for specific reporting period}}{\text{Total Person years for specific reporting period}}$$

The following participant-level listings will be generated for AE data:

- All AEs
- All SAEs
- AEs leading to study drug discontinuation
- AEs leading to death
- AEs of special interest

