## **6.2. Appendix 2: Technical Specifications for Derived Variables**

### **6.2.1. Derivation of Treatment-emergent Adverse Events for Missing or Incomplete Date of Onset**

If both start and end dates of AEs are completely missing, no imputation will be performed, and those AEs will be considered treatment-emergent.

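### SAP Table 5 places adverse events by onset alone, so one that starts on placebo and becomes serious or fatal after the Week 50 switch can be missing from the OLE tables

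*SAP*

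**What the plan says.** SAP 5.6.2, Table 5, defines treatment-emergent AEs (TEAEs) separately for the two periods. For the OLE: "A TEAE will be defined as any AE with onset on or after first dose of OLE". For RCP participants who enter the OLE, onset must lie between the first RCP dose and a cut-off, "up to and including the day prior to the first OLE dose". The time-of-day rule below the table and the rule for pretreatment AEs also work from onset. Protocol 9.4.6.1 does the same, with a treatment-emergent AE "defined as an AE with onset on or after first dose of study drug administration in the Randomized Controlled Period".

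The one exception to onset is in SAP 6.2.1: "If both start and end dates of AEs are completely missing, no imputation will be performed, and those AEs will be considered treatment-emergent".

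On severity, SAP 5.6.2 says that "if the same AE occurs multiple times for a participant, the highest severity and relationship to IP observed will be reported".

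On recording, Protocol 10.3.3 says "New or updated information will be recorded in the originally completed eCRF" and also "Changes in the severity of an AE should be documented to allow an assessment of the AE duration at each level of intensity".

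SAP Table 6 keeps six OLE summaries: overall TEAEs; TEAEs by system organ class and preferred term; serious TEAEs (TESAEs); nonserious TEAEs; TEAEs leading to withdrawal; and TEAEs leading to death. Each is shown for Ravulizumab/Ravulizumab, Placebo/Ravulizumab and Total.

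**The concern.** Week 50 is the placebo group's first exposure to C5 inhibition. Protocol Table 4 lists meningococcal infection as an identified risk and serious infection as a potential one. The six OLE tables are where events after that first exposure are counted for former placebo patients.

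With an onset-only rule, an AE already present at the switch stays with the placebo period whatever happens to it afterwards. If it then becomes serious or fatal, the OLE TESAE or death table does not count it. The SAP also does not say that RCP tables stop taking information at the first OLE dose, so the later seriousness could be shown as a placebo event.

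**Working it through.** This is mainly a check of text. The plan gives no figure to reproduce.

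**1. Is there a worsening rule?** Table 5, the time-of-day rule, the pretreatment rule, SAP 6.2.1 and Protocol 9.4.6.1 contain none. The highest-severity sentence in SAP 5.6.2 covers an AE that occurs more than once. It neither re-dates onset nor sets a cut-off at the first OLE dose.

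**2. One record or two?**
- Towards one record: Protocol 10.3.3 sends updates to the original eCRF entry, and 10.3.4 asks for the electronic record to be updated when more information on a serious AE arrives.
- Room for a second record: 10.3.3 wants duration at each intensity level, which implies dated segments. Protocol 10.3.1 counts exacerbation of a pre-existing condition as an AE. It does not say whether this covers an on-study AE still open at Week 50.
- Outside the concern: "New conditions detected or diagnosed after study drug administration" are AEs in their own right under 10.3.1. A new diagnosis after the switch has its own onset and is counted in the OLE.
- The eCRF completion rules are not in the documents.

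**3. Trace, assuming one record.** A patient has a grade 1 AE starting in Week 48, and it becomes serious after the Week 50 dose.

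| | Randomized to placebo | Randomized to ravulizumab |
|---|---|---|
| TEAE (RCP)? | Yes: onset before first OLE dose | Yes |
| TEAE (OLE)? | No: onset before first OLE dose | No |
| OLE TESAE table | Not counted under Placebo/Ravulizumab | Not counted under Ravulizumab/Ravulizumab |
| RCP tables | May show later seriousness under placebo | May show later seriousness under ravulizumab |
| AE and SAE listings | Shown | Shown |

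The carry-over into the RCP is the same in both columns. At 2:1, the planned 354 give 354 × 2/3 = 236 ravulizumab and 354/3 = 118 placebo patients.

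**4. Size per patient.** SAP 5.6.2 counts each participant once per row.
- OLE Placebo/Ravulizumab row: change = 0 if the patient already has another event in that row, otherwise 1/n, with n the number of switchers. The documents do not give n. For illustration: 1/12 = 8.3 percentage points, 1/30 = 3.3, 1/39 = 2.6. The values 12 and 30 are assumptions (about 10% and 25% of 118).
- The value 39 also rests on an assumption. A patient at Week 50 by 18 Nov 2021 (SAP version 2) had reached Week 26 24 weeks (168 days) earlier, about 3 Jun 2021. If the 33% interim trigger had not been met by then, fewer than 0.33 × 354 = 117 patients had completed Week 26, and 117/3 = 39 of them would be placebo.
- RCP rows, at planned size: 0 or 1/118 = 0.85 points for placebo; 0 or 1/236 = 0.42 points for ravulizumab.

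**5. Chance of any such case.** The chance is 1 − (1 − p)^n. The documents give no p; 1% and 5% are assumed.

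| n | p | Expected count | Chance of at least one |
|---|---|---|---|
| 12 | 0.01 | 0.12 | 0.11 |
| 12 | 0.05 | 0.60 | 0.46 |
| 39 | 0.01 | 0.39 | 0.32 |
| 39 | 0.05 | 1.95 | 0.86 |

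The spread shows how little the documents fix this number.

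**The case against.** The strongest reply is that the harm depends on a source the reader cannot see. If the eCRF rules open a new record at each worsening, Table 5 already works. This stands as a condition on the point. It does not remove it, because the SAP should be readable without that source and currently does not state the convention.

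Other replies that stand:
- No OLE table is by severity. A grade increase alone would show only as a counted TEAE, so the loss matters for the TESAE, withdrawal and death tables.
- Week 50 has safeguards. Examination, vital signs and laboratory tests are scheduled, drug is given after all other procedures, and safety concerns are to be raised with the sponsor. These lower the chance of dosing through an active illness but do not decide where a later worsening is counted.
- The bound of 39 is weak. It reads the future tense in Protocol 9.5 (Amendment 6, 23 Jun 2021) as evidence of timing, yet SAP version 2 still calls the interim planned after the futility criterion was met.

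Three stronger readings might be inferred, and the documents support none of them. The first is that the rule tilts the randomized comparison towards ravulizumab: the same carry-over applies to both arms, so no net direction is shown. The second is that a missed patient moves an OLE row by at least 2.6 points: with once-per-participant counting the change can be 0. The third is that new serious infections after the switch would be missed: a new diagnosis is a new AE.

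**Conclusion.** The point holds in conditional form. Read literally, Table 5 leaves out of the OLE TESAE, withdrawal and death tables a continuous AE that starts on placebo and reaches that outcome after the first ravulizumab dose. It also leaves open whether RCP tables show the post-switch outcome. Both consequences require that such an AE is one record with its first onset date, which Protocol 10.3.3 suggests but does not settle.

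The size is probably small and cannot be fixed from the documents, because the number of switchers and the event rate are both unknown. SAP 5.1 makes p-values and confidence intervals descriptive, SAP 5.6 makes the safety analyses descriptive, and SAP 6.4 calls the OLE data small. The listings let a reader find each case. Minor priority.

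**What to change.** In SAP Table 5:
- Add to TEAE (OLE): *or an AE with onset before the first OLE dose that increases in grade or becomes serious (including fatal) on or after that dose*. If the withdrawal table is meant to be complete, also name an AE that first leads to withdrawal after that dose, since this can happen with no change in grade or seriousness.
- Add to TEAE (RCP): *or an AE with onset before the first RCP dose that increases in grade or becomes serious on or after that dose and, for participants entering the OLE, before the first OLE dose*. Limit this to AEs not already recorded as new under the exacerbation rule in Protocol 10.3.1.
- State that, for participants in both arms who enter the OLE, RCP tables use only severity, seriousness and outcome observed before the first OLE dose.

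Record the departure from Protocol 9.4.6.1 in SAP 6.4. If the eCRF rules already open a new record at each worsening, say so in SAP 5.6.2; the clauses then change nothing.

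The cost is a few lines of text and a change to the AE derivation before final database lock, using severity changes that sites must already document. There are three downsides. One AE can appear in both periods' tables. The date of becoming serious must come from the SAE record. And because the OLE has no placebo comparator, worsening from unrelated illness will also be counted; expected ALS progression is mostly kept out by the AE definition in Protocol 10.3.1.

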**Table 6: Overview of Adverse Event Analysis by Study Period**

Type of Analysis	Period Analysis Set Treatment Group Display Convention			Additional Notes
	Screening SS Ravulizumab, Placebo, Total	RCP SS Ravulizumab, Placebo	OLE OLES Ravulizumab/Ravulizumab, Placebo/Ravulizumab, Total	
Overall summary of TEAEs		X	X	
TEAEs by SOC and PT		X	X	
TESAEs by SOC and PT		X	X	
Nonserious TEAEs by SOC and PT		X	X	
TEAEs leading to study drug withdrawal by SOC and PT		X	X	
TEAEs leading to death by SOC and PT		X	X	
TEAEs by SOC and PT by highest relationship to IP		X		Relationship to IP: related, not related
TEAEs by SOC, PT, and highest severity		X		Severity: Grade 1, 2, 3, 4, and 5
TEAEs (IP-related) by SOC, PT, and highest severity		X		
TEAEs (IP-related) by SOC and PT		X		
TESAEs (IP-related) by SOC and PT		X		
TESAEs by SOC, PT, and highest relationship to IP		X		Relationship to IP: related, not related
TEAEs (≥ 1%) by SOC and PT		X		≥ 1% in all participants
TEAEs by SOC sorted by decreasing frequency		X		Decreasing frequency by ravulizumab arm (RCP), all participants (OLE)
TEAEs by PT sorted by decreasing frequency		X		
TESAEs by PT sorted by decreasing frequency		X		

**Table 6: Overview of Adverse Event Analysis by Study Period**

Type of Analysis	Period Analysis Set Treatment Group Display Convention			Additional Notes
	Screening SS Ravulizumab, Placebo, Total	RCP SS Ravulizumab, Placebo	OLE OLES Ravulizumab/Ravulizumab, Placebo/Ravulizumab, Total	
TEAEs (IP-related) by PT sorted by decreasing frequency		X		
AESI by SOC and PT		X		AESI: Meningococcal infection
Infusion reaction related TEAEs by SOC and PT		X		
Infusion reaction related TESAEs by SOC and PT		X		
Infusion reaction related TEAEs (IP related) by SOC and PT		X		
Overall Summary of COVID-19 related TEAEs		X		
COVID-19 related TEAEs by SOC and PT		X		
COVID-19 related TESAEs by SOC and PT		X		
AEs during Screening Period by SOC and PT	X			

Abbreviations: AE = adverse event; AESI = adverse event of special interest; IP = investigational product; OLE = Open-Label Extension; OLES = Open-Label Extension Set; PT = preferred term; RCP = Randomized Controlled Period; SOC = system organ class; SS = Safety Set; TEAE = treatment-emergent adverse event; TESAE = treatment-emergent serious adverse event

### 5.6.3. Laboratory Tests

The analysis of central laboratory parameters (hematology, clinical chemistry, and urinalysis) will be summarized descriptively. Laboratory results based upon standardized units will be used for analyses. The last record will be used if there are multiple records of laboratory measurements at Baseline or post-Baseline Visits. The following analyses will be performed:

- Actual laboratory results, baseline values, and changes from Baseline will be summarized using descriptive statistics (mean, SD, etc.) for each scheduled study visit and for the last visit within each period for the respective laboratory parameter.
- Shift analyses will be conducted by calculating the number and percentage of participants in the low, normal, and high category combinations at both Baseline and post-Baseline Visits; the total number of participants with nonmissing values at both Baseline and post-Baseline Visits will be used as the denominator for the percentage calculation.
- The number (%) of participants meeting the criteria in [Table 7](#) for the liver function-related laboratory values (alanine aminotransferase [ALT], aspartate aminotransferase [AST], alkaline phosphatase [ALP], and total bilirubin [TBL]) will be provided.

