### **8.3.8. Clinical Safety Laboratory Assessments**

- See Section 10.2 for the list of clinical laboratory tests to be performed and the SoA (Section 1.3 for the timing and frequency).
- The Investigator must review the laboratory report, document this review, and record any clinically relevant changes occurring during the study in the AE section of the eCRF. The laboratory reports must be filed with the source documents. Clinically significant abnormal laboratory findings are those which are not associated with the underlying disease, unless judged by the Investigator to be more severe than expected for the patient's condition.
- All laboratory tests with values considered clinically significantly abnormal during participation in the study or within 8 weeks after the last dose of study drug should be repeated until the values return to normal or baseline or are no longer considered clinically significant by the Investigator or medical monitor.
  - If such values do not return to normal/baseline within a period of time judged reasonable by the Investigator, the etiology should be identified and Alexion notified.
  - All protocol-required laboratory assessments, as defined in Section 10.2, must be conducted in accordance with the Laboratory Manual and the SoA.
  - If laboratory values from non-protocol specified laboratory assessments performed at the institution's local laboratory require a change in patient management or are considered clinically significant by the Investigator (eg, serious adverse event (SAE) or AE or dose modification), then the results must be recorded in the CRF.

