#### 5.6.4. Vital Signs

The analysis of the following vital signs will be summarized descriptively: systolic blood pressure (mmHg), diastolic blood pressure (mmHg), heart rate (beats/min), respiratory rate (breaths/min), weight (kg), and temperature (°C).

If there are multiple records of vital sign measurements at Baseline or post-Baseline Visits, the last record will be used. The following analyses will be performed:

- Actual vital sign measurements, baseline values, and changes from Baseline will be summarized using descriptive statistics (mean, SD, etc.) for each scheduled study visit.
- The number (%) of participants meeting the potentially clinically significant abnormality criteria (Table 9) at least once during the RCP will be provided.

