### 5.6.5. Electrocardiogram

The analysis of the following ECG measurements will be summarized descriptively: heart rate (beats/min), PR interval (msec), QRS duration (msec), RR interval (msec), QT interval (msec), corrected QT interval by Fridericia (QTcF; msec), and overall interpretation.

If there are multiple records of ECG measurements at Baseline or post-Baseline Visits, the last record will be used. The following analyses will be performed:

- Actual ECG measurements, baseline values, and changes from Baseline will be summarized using descriptive statistics (mean, SD, etc.) for each scheduled study visit
- The number (%) of participants with abnormal ECG findings (normal, abnormal – not clinically significant, and abnormal – clinically significant).
- The number (%) of participants meeting the potentially clinically significant abnormality criteria (Table 11) for QT and QTcF at least once during the RCP will be provided.

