**6.2.9.1. Rules for Selecting the Analysis Records**

Only 1 record per analysis window will be selected for analysis. The following defines the selection rule.

1. Only scheduled visits of the specific endpoint will be selected and summarized in the tables and figures. If the earlier versions of the protocol and the final version of the protocol have different assessment schedules, then both scheduled visits will be used for the descriptive summary, as appropriate. Only the scheduled visits in the latest protocol will be selected for inferential analysis.
  - a. For example, an unscheduled SVC assessment may fall into the Week 22 analysis window. However, because Week 22 is not a scheduled visit for SVC, this record will not be flagged for descriptive and inferential analysis.
2. If there are multiple non-missing records within the same analysis window, the record closest to the target day will be selected.
3. If there are records with equal distance from the target day, the later record will be selected.
4. For CAFS analysis, only the last nonmissing record of ALSFRS-R will be selected.

Similar visit windows will be implemented for the OLE Period.

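### The SAP gives two rules for choosing among several post-baseline lab, vital-sign or ECG records in one window, with no precedence, and its scheduled-visit filter read literally trims the counts meant to catch any abnormality

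*SAP*

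**What the plan says.** The three safety sections share one rule. SAP 5.6.3: "The last record will be used if there are multiple records of laboratory measurements at Baseline or post-Baseline Visits". SAP 5.6.4: "If there are multiple records of vital sign measurements at Baseline or post-Baseline Visits, the last record will be used". SAP 5.6.5: "If there are multiple records of ECG measurements at Baseline or post-Baseline Visits, the last record will be used".

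SAP 6.2.9.1 allows one record per analysis window. Rule 1: "Only scheduled visits of the specific endpoint will be selected and summarized in the tables and figures"; its example leaves an unscheduled SVC record unflagged for both descriptive and inferential analysis. Rule 2: "If there are multiple non-missing records within the same analysis window, the record closest to the target day will be selected". Rule 3: "If there are records with equal distance from the target day, the later record will be selected". Rule 4 makes an exception for CAFS and for nothing else.

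Protocol 8.3.8 says that clinically significantly abnormal laboratory values "should be repeated until the values return to normal or baseline or are no longer considered clinically significant by the Investigator or medical monitor".

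The abnormality counts differ by domain:
- **ALT and AST (SAP Table 7):** single-analyte thresholds by scheduled visit and also on any post-baseline value.
- **Combined ALT with bilirubin (and ALP) criteria (SAP Table 7):** by scheduled visit only.
- **Vital signs (SAP 5.6.4):** participants who meet a criterion at least once in the Randomized Controlled Period (RCP).
- **QT and QTcF (SAP Table 11 note):** the maximum post-baseline value or change.

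**The concern.** One rule goes by order in time and the other by distance from a target day. Nothing limits 6.2.9.1 to efficacy data, and nothing says that 5.6.3 to 5.6.5 override it. Two programmers could each follow the SAP faithfully and produce different tables.

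By-visit summaries, laboratory shift tables and box plots, and the by-visit liver criteria are exposed. The combined ALT/bilirubin criteria matter most, because they have no count over all post-baseline values to fall back on.

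There is a second gap. If rule 1 governs every table, an abnormal value from an unscheduled draw is left out even of counts worded to capture any abnormality. Efficacy results are now descriptive only (SAP 5.1), so safety reporting carries much of what the trial can still contribute.

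**Working it through.** No figure in the plan needs reproducing. The check compares the rules and then applies them to the SAP Table 23 windows.

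**1. Baseline.** SAP Tables 8, 10 and 12 define baseline as the last nonmissing value before the first RCP infusion. The last-record rule agrees with that, so any conflict is post-baseline.

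**2. How long two records can share a window.** Upper limit minus target day:
- Week 2: 29 − 15 = 14
- Week 10: 85 − 71 = 14
- Week 18: 141 − 127 = 14
- Week 26: 211 − 183 = 28
- Week 34: 267 − 239 = 28
- Week 42: 323 − 295 = 28

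A second record up to 14 or 28 days after an on-target visit therefore stays in the same window. Beyond 14 days at Weeks 2, 10 and 18 it falls in the Week 6, 14 or 22 window, where no labs are scheduled.

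**3. A case that rule 1 does not clearly remove.** The ED visit is in the protocol's schedule (Table 1, Week 50/ED column) with labs, vital signs and ECG. Under Protocol 7.2 it takes place no later than 8 weeks after the last dose. Take a Week 26 visit and dose on Day 183 and an ED visit on Day 200. The gap is 17 days, and both dates lie in the Week 26 window (Days 170 to 211). The last-record rule takes Day 200. Rule 2 takes Day 183, at distance 0 rather than 17. The same can occur at other weeks for labs and vital signs. ECG is scheduled in the RCP only at Week 26 and Week 50/ED, so for ECG the Week 26 window is the relevant one.

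**4. How often the rules disagree when both records are eligible.** Let the scheduled draw fall on any day s in the protocol visit window (target ± 2 days at Week 2, ± 3 days at the others). Let the second record fall on any later day r up to the window's upper limit. The rules agree only when r is at least as close to target as s. For s that is k days before target, this gives 2k values of r; for s on or after target, none.

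| Week | Pairs | Agree | Differ |
|---|---|---|---|
| 2 | 16+15+14+13+12 = 70 | 2+4 = 6 | 64 (91%) |
| 10, 18 | 17+16+15+14+13+12+11 = 98 | 2+4+6 = 12 | 86 (88%) |
| 26, 34, 42 | 31+30+29+28+27+26+25 = 196 | 2+4+6 = 12 | 184 (94%) |

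This counts day-pairs with equal weight and does not forecast how often they occur. Rule 2 does not always keep the first value either: a draw on Day 180 and a second on Day 185 give Day 185 under both rules.

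**5. Direction.** A retest of a clinically significant abnormal lab continues until it is normal, back to baseline or no longer clinically significant. If it is filed under the scheduled visit, the last record tends to be the resolved one. An ED value is not a retest made until recovery, so nothing fixes its direction. The retest provision covers laboratory tests only.

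**6. Rule 1 on a late repeat.** Suppose neutrophils are low on Day 183 and normal on an unscheduled repeat on Day 204. Day 204 is outside Day 183 ± 3. If rule 1 applies, the repeat is dropped and the low value stands. If 5.6.3 is read as overriding rule 1, the normal value is reported for Week 26. The SAP does not say which.

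**The case against.** The best defence is that the rules can be read together: select the visit closest to target, then the last record at that visit. Sections 5.6.3 to 5.6.5 speak of visits and rule 2 speaks of windows. Same-day duplicates are equally distant from target, so rule 3 picks the later one, as the last-record rule does. This reading is sensible, but the SAP does not state it. SAP 6.2.9 maps actual dates to analysis visits, so a visit in the output is itself a window. The conflict over two dates in one window stands.

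A reader might go further and infer that labs must be repeated until normal, that the last-record rule is therefore biased toward normal by design, and that abnormalities vanish from every summary table. The documents do not support this:
- Protocol 8.3.8 says should, applies only to clinically significantly abnormal values, and lets repeats stop short of normal. A last repeat can still be out of range.
- A late repeat is normally unscheduled, and rule 1 would exclude it. Replacement needs the repeat to be filed under the visit, or 5.6.3 to override rule 1.
- Protocol 8.3.8 has clinically relevant laboratory changes recorded as adverse events, so they can reach the TEAE tables.
- The ALT/AST, vital-sign and QT/QTcF counts are worded to keep the worst value.

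All four points stand and limit the concern. The last is incomplete, because the SAP does not say whether those counts use all records or only those that survive rule 1.

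**Conclusion.** The conflict is real for post-baseline laboratory, vital-sign and ECG records, and no precedence is stated. Where two eligible records share a window, the rules choose different ones in 88% to 94% of possible day-pairs. The number of affected participants cannot be estimated, because the documents give no frequency for retests or for ED visits that share a window.

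Replacement of an abnormal value by a recovered one is conditional on how a retest is filed and on whether rule 1 governs 5.6.3. It is a possible consequence, not a built-in one. For ED visits the effect is of unknown direction.

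Two gaps do not depend on the retest argument. Rule 1, taken literally, removes unscheduled abnormal values from counts intended to capture any abnormality. The combined ALT/bilirubin criteria are counted by scheduled visit only. The point is worth settling before the final database lock, the deadline SAP section 1 sets for finalizing this amendment. It casts no doubt on the safety data collected, only on how they are tabulated.

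**What to change.** Amend the SAP in three places:

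1. In 5.6.3 to 5.6.5, limit the last-record rule to Baseline and to duplicates on the same day.
2. State that post-baseline by-visit tables, shift tables and box plots follow 6.2.9.1: the scheduled record closest to the target day, with the later one on a tie.
3. Exempt from rule 1 the ALT/AST counts on any post-baseline value, the vital-sign counts of at least one occurrence in the RCP, the QT/QTcF maximum, and the combined ALT/bilirubin(/ALP) criteria. Base all of these on every post-baseline record, including repeat, ED and unscheduled ones. This adds to Table 7 an any-post-baseline count for the combined criteria, still judged on a single sample.

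The cost is a few sentences and some programming on data already collected. Reported abnormality rates may come out slightly higher.
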